19.3. Enrollment Sample Size

The maximum sample size for primary safety and efficacy is that of primary safety or 140 subjects required at 30 days. Conservatively, correcting that number for approximately 12.5% attrition at 30 days requires enrollment of 160 subjects. With 160 subjects enrolled and accounting for 20% attrition by 1 year, it is expected that 128 subjects will be evaluable for primary efficacy at 1 year providing 96 to 99% power depending on the proportion enrolled in each disease state.

19.4. Study Success

The study will be considered a success if the primary safety endpoint is met in either the SARS-CoV-2 negative subset or all subjects and the primary efficacy endpoint is met in either the SARS-CoV-2 negative subset or all subjects. The Type I error for testing in both the SARS-CoV-2 negative subset and all subjects will be controlled using the Hochberg correction.

19.5. Administrative Reports and Interim Reports

An administrative report will be completed upon completion of enrollment to fix the performance goal for primary efficacy. The study will enroll subjects from each of three disease states, i.e. nonthrombotic, acute thrombotic, and chronic postthrombotic. The study will require that at least 20% of the subjects are enrolled in each of the disease states. The PG for the primary efficacy objectives depends on the proportion of ITT subjects in each disease state. Once enrollment is completed, the proportion of ITT subjects with nonthrombotic, acute thrombotic, and chronic postthrombotic disease will be calculated. The proportions are the weights in the formula to calculate the PG. The calculation is described in **Section 19.11**, “Primary Efficacy Objective”. The PG for primary efficacy will be fixed in advance of or prospectively to the efficacy analyses. There is no Type I error adjustment for this report given that no hypotheses will be tested.

The study data may be summarized prior to the time at which all N=160 enrolled subjects complete 12 months of follow-up or exit the study early to fulfill an EU MDD post-market approval requirement for CE Mark. Since the interim look at the data set will not be used to claim early trial success with the FDA or to modify the study design, no correction to Type I error is required. Because of the potential to introduce bias into the study given knowledge of the interim results, Vesper Medical will create a standard operating procedure outlining the measures that will be taken to mitigate the risk of bias. Main measures will include: identifying the roles within the company who have visibility to the data, the security measures in place for storing the data, commitment

that no data will be shared with investigational sites until the full cohort is analyzed at 12 months and that the interim results will not be shared publicly via podium or publication.

19.6. Pooling Evaluation

The investigational sites will be tested for differences in the primary safety endpoint and primary efficacy endpoint in the FAS subset using Fisher's Exact test for both the SARS-CoV-2 negative subset and all subjects. Subjects will be stratified by disease state to evaluate pooling for primary efficacy and not stratified for primary safety. The Fisher's Exact test will be performed 4 times, once for each disease state for primary efficacy and once for primary safety.

Investigational sites with less than 10 subjects per disease state will be combined for the purpose of the pooling evaluation with respect to the primary efficacy endpoint. In chronological order of site participation, sites with less than 10 subjects per disease state will be aggregated until the pseudo-site reaches >10 subjects per disease state. Once that happens a second pseudo-site will be created, etc. If the final pseudo-site is less than 10 subjects per disease state it will be combined with the previous pseudo-site. Additionally, the poolability analysis will be conducted with ONLY sites with 10 or more subjects in each disease etiology.

Investigational sites with less than 10 subjects overall will be combined for the purpose of the pooling evaluation with respect to the primary safety endpoint. In order of site participation, sites with less than 10 subjects will be aggregated until the pseudo-site reaches >10 subjects. Once that happens a second pseudo-site will be created, etc. If the final pseudo-site is less than 10 subjects it will be combined with the previous pseudo-site. Additionally, the poolability analysis will be conducted with ONLY sites with 10 or more subjects.

If there are any investigational site effects (i.e., statistically significant results at two-sided $p < .15$), a random center effect will be included in a logistic regression model to assess the primary objective. If there are no differences, the data from all investigational sites will be pooled for the analyses.

Additionally, the primary safety and efficacy endpoints will be summarized by US and OUS centers. The study was not powered to demonstrate the primary efficacy and safety endpoints within the subgroups defined by geography and therefore it is not an expectation that the primary safety and efficacy endpoint will be statistically significant within the subgroups determined by geography.

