H₁: Proportion of subjects with freedom from MAE is greater than the (PG) at 30 days, $p_{MAE} > 89\%$

The freedom from MAE proportion will be calculated such that the numerator is the number of subjects in whom a MAE did not occur within 30 days of the index procedure. The denominator is the number of subjects with 30 days of follow-up plus the number of subjects with a MAE prior to 30 days who exited the study prior to 30 days, if any.

Sample Size Rationale: Using PASS 19, a one-sample Exact Test (binomial enumeration), power = 90%, one-sided Type I error controlled at 2.5%, and assumed freedom from MAE of 96.1% with a PG goal of 89%, the required evaluable sample size is 140 subjects.

Primary Statistical Analysis: The primary statistical analysis will be conducted in the FAS subset for the primary safety endpoint overall and in the SARS-CoV-2 negative subset. The primary statistical method is a one-sample exact test comparing the proportion of subjects free from a MAE to the PG using a two-sided $\alpha = 0.05$. The exact two-sided 95% confidence interval for the proportion of subjects free from MAE will be calculated.

The two-sided p-value in the SARS-CoV-2 negative subgroup and all subjects will be calculated and ordered from largest to smallest. If the largest p-value, is statistically significant at $p < 0.05$ then the hypothesis test is statistically significant in both the SARS-CoV-2 negative subset and all subjects. If not, testing continues to the smallest p-value. If the smallest p-value < 0.025 then the hypothesis test is statistically significant in the group for which the smallest p-value is associated with. If the

¹ Razavi MK, Jaff MR, Miller LE. Safety and Effectiveness of Stent Placement for Iliofemoral Venous Outflow Obstruction Systematic Review and Meta-Analysis. Circ Cardiovasc Interv. 2015;8:e002772. DOI: 10.1161/CIRCINTERVENTIONS.115.002772.)

smallest p-value ≥ 0.025 , then the hypothesis test is not statistically significant in either the SARS-CoV-2 negative subset nor all subjects.

Additional Analysis: The evaluation for pooling analyses specified in **Section 19.6** will be completed. If there is missing data for the ITT subjects, the sensitivity to missing data analysis outlined in **Section 19.7** will be completed. Additionally, the primary statistical analysis will be conducted in the per protocol sample overall and in the SARS-CoV-2 negative subset.

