Sample Size Rationale: With an expected FAS sample size of N=128, one-sided Type I error less than or equal to 2.5%, and assumed primary patency at 12 months equal to .96, .87, .79, i.e. the point estimates for primary patency from Razavi et al for nonthrombotic, acute thrombotic, and chronic postthrombotic respectively, the power for primary efficacy ranges from 96 – 99% depending on proportion in each disease-state given a minimum of at least 20% in each group. The table below provides the matrix of simulated power varying the ITT proportions for the disease states.

Power Calculations Using Simulation for the Primary Statistical Analysis

Proportion of Subjects Expected in Each Group			Assumed Freedom from Primary Efficacy				Calculated Performance Goal				Power at N=128 Evaluable (20% attrition for N=160 enrolled)
NT	AT	CPT	NT	AT	CPT	Pooled	NT	AT	CPT	PG	One-sided Type I error = 2.5%
0.3333	0.3333	0.3333	0.96	0.87	0.79	0.873	0.83	0.7	0.66	0.73	98%
0.2	0.2	0.6	0.96	0.87	0.79	0.84	0.83	0.7	0.66	0.702	96%
0.2	0.6	0.2	0.96	0.87	0.79	0.872	0.83	0.7	0.66	0.718	99%
0.6	0.2	0.2	0.96	0.87	0.79	0.908	0.83	0.7	0.66	0.77	96%
0.3	0.3	0.4	0.96	0.87	0.79	0.865	0.83	0.7	0.66	0.723	97%
0.3	0.4	0.3	0.96	0.87	0.79	0.873	0.83	0.7	0.66	0.727	99%
0.4	0.3	0.3	0.96	0.87	0.79	0.882	0.83	0.7	0.66	0.74	98%
0.4	0.4	0.2	0.96	0.87	0.79	0.89	0.83	0.7	0.66	0.744	99%
0.4	0.2	0.4	0.96	0.87	0.79	0.874	0.83	0.7	0.66	0.736	98%
0.2	0.4	0.4	0.96	0.87	0.79	0.856	0.83	0.7	0.66	0.71	98%

Primary Statistical Analysis: The primary statistical analysis will be conducted in the FAS subjects overall and in the SARS-CoV-2 negative subgroup. The primary statistical comparison will use a one-sample Z-test comparing the proportion of subjects with primary patency to the PG using a one-sided $\alpha = 0.025$ equivalent to a z-score of 1.96. The variation in the proportion will be estimated using the disease-specific performance goals themselves, i.e. under the null, rather than use the estimated patency rates, i.e. under the alternative.

The estimates that will be observed for primary patency in each disease etiology are noted as follows:

$\hat{p}_{p_pat_NT}$ = The primary patency observed in the NT subjects.
 $\hat{p}_{p_pat_AT}$ = The primary patency observed in the AT subjects.
 $\hat{p}_{p_pat_CPT}$ = The primary patency observed in the CPT subjects.

The percent of subjects in the FAS with each disease etiology are noted as follows:

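### Section 19.6 does not settle whether a random-centre logistic model replaces the primary tests after a pooling result of p<0.15, and that model's intercept is not the proportion of subjects in the hypotheses

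*Combined protocol and SAP*

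**What the plan says.** **Section 19.6 (Pooling Evaluation).** Sites are compared on each primary endpoint: "The Fisher's Exact test will be performed 4 times, once for each disease state for primary efficacy and once for primary safety". This is done for all subjects and for the SARS-CoV-2 negative subset, after small sites have been merged into pseudo-sites. If any site effect reaches two-sided p<0.15, "a random center effect will be included in a logistic regression model to assess the primary objective". Otherwise, "If there are no differences, the data from all investigational sites will be pooled for the analyses".

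**Section 19.10 (Primary Safety Objective).** The alternative hypothesis is "Proportion of subjects with freedom from MAE is greater than the (PG) at 30 days", with a PG of 89%. "The primary statistical method is a one-sample exact test comparing the proportion of subjects free from a MAE to the PG". The pooling evaluation appears later, under Additional Analysis.

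**Section 19.11 (Primary Efficacy Objective).** The hypothesis again concerns a proportion of subjects. The PG is a weighted mix of 0.83, 0.70 and 0.66 for the three disease states. The estimate is weighted by disease state, and for the Z-test "The variation in the proportion will be estimated using the disease-specific performance goals themselves". The pooling evaluation follows the primary test, alongside the Kaplan-Meier, missing-data and per-protocol analyses.

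No section states which parameter of the logistic model is tested, with which test, how either PG enters it, or whether a trigger in one disease state changes the whole efficacy analysis.

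**The concern.** Section 19.6 reads most naturally as a switch: one analysis of the primary objective if sites differ, another if they do not. Sections 19.10 and 19.11 read as though the primary test never changes. Both cannot govern the success decision.

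The conflict matters because the two analyses need not answer the same question. The hypotheses concern the proportion of all subjects who succeed. The fixed intercept of a random-intercept logistic model describes a site in the middle of the distribution of sites. When success rates are above 50% and sites vary, that rate is higher than the average over sites. For efficacy there is a further gap: the PG depends on disease mix, and nothing in Section 19.6 carries the disease weights or the null variance into the model.

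At stake is a pass or fail against a fixed PG in a single-arm trial, decided by choices that could still be made after the data are seen.

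**Working it through.** **1. The plan's own safety figure.** Inputs from Section 19.10: "one-sided Type I error controlled at 2.5%, and assumed freedom from MAE of 96.1% with a PG goal of 89"%, 90% power, 140 evaluable subjects. Exact binomial: success needs at least 132 of 140 free of MAE. P(X≥132 | 0.89) = 0.0240 and P(X≥132 | 0.961) = 0.902. Enrolment: 140/(1−0.125) = 160. The plan's figures reproduce. With 131 of 140 the one-sided p is 0.048, a fail.

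**2. Median-site rate against subject proportion.** Let site log-odds be b + u, with u normal, mean 0, SD s. The marginal proportion is p = ∫ expit(b + s·z) φ(z) dz, and the median-site rate is expit(b). Set p equal to the PG and solve for b. The efficacy PG for an equal disease mix is (0.83 + 0.70 + 0.66)/3 = 0.73, as in the first row of the plan's power table. The SDs are assumptions.

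| Assumed SD (log-odds) | Median-site rate, true 89% | Median-site rate, true 73% |
|---|---|---|
| 0.5 | 89.9% (b = 2.186) | 74.1% (b = 1.050) |
| 0.71 | 90.7% (b = 2.278) | 75.0% (b = 1.101) |
| 1.0 | 92.0% (b = 2.447) | 76.7% (b = 1.193) |

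In every row the null is true, yet the intercept lies above the PG.

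**3. A worked safety data set.** Take 131/140 free of MAE, at 20 sites of 7, with the nine failures at five sites (2, 2, 2, 2, 1). Maximum likelihood gives an intercept of 3.504 (standard error 0.924) and a site SD of 1.49.

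- Median-site rate: expit(3.504) = 97.1%.
- Averaged over sites: 93.5%, against 93.6% observed.
- Wald: (3.504 − logit 0.89)/0.924 = (3.504 − 2.091)/0.924 = 1.53, a fail at 1.96.
- Signed likelihood-ratio z = 2.44, a pass.

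So the same model on the same data passes or fails according to the test chosen. Averaging over sites removes the gap in the estimate. Whether the switch fires also depends on site order, because sites of 7 pair into pseudo-sites of 14. If the failing sites are consecutive (4, 4, 1, then zeros), Fisher p is below 0.001. If each is paired with a clean site, a simulated Fisher p (50,000 random allocations of nine failures) is about 0.23 and there is no switch.

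**4. False success under the two-step rule.** Simulated safety trials, SD 1.0, 140 subjects, PG 89%, nominal 2.5%:

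| How the null was set | Likelihood ratio | Wald | Pooled exact |
|---|---|---|---|
| Each trial's subject proportion fixed at 89%; three site layouts | 6.1-7.1% | 1.0-1.6% | within 0.7-2.5%* |
| Site effects drawn at random, marginal rate 89%; 30 unequal sites | 10.4% | 3.8% | 5.2% |

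*Range over both endpoints at SD 1.0 and 1.5.

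At SD 0.5 with random site effects: likelihood ratio 5.2%, Wald 3.0%, pooled exact 4.1%. For efficacy at SD 1.0 (first null setting; simplified to 140 subjects and one PG of 0.73, without disease strata): likelihood ratio 1.8-4.9%, Wald 1.3-1.9%. Monte Carlo error is roughly 0.3 to 0.6 points.

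**5. Direction.** At SD 1.0 with larger sites doing better, the mean model estimate after a trigger was 67.6% against 73.0% pooled (efficacy) and 88.9% against 88.8% (safety). With larger sites doing worse, likelihood-ratio false success was 9.2% (safety) and 19.0% (efficacy).

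**6. How often the switch fires.** With no site differences, about 12-16% of trials per test. For three independent efficacy tests at exactly 0.15 the chance of at least one is 1 − 0.85³ = 39%. At SD 1.0 each test fires in 30-82% of trials, depending on layout and endpoint.

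**The case against.** The strongest reply is that this is missing detail and no more. Sections 19.10 and 19.11 name the primary tests unconditionally and place pooling among the additional analyses, so the model may only be supportive. Nothing says that the intercept is what gets tested; a site-averaged estimate from the same model would answer the right question. Nor does the plan say that disease terms would be left out. All of that stands, and it rules out stating replacement as fact.

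A reader might infer that the primary test becomes one of a typical-site rate, and that it overstates success exactly when sites differ. The documents do not support that. They specify neither replacement nor the tested parameter. With a Wald test the two-step rule gave fewer false successes for safety at SD 1.0 than the pooled exact test in the random-site simulation (3.8% against 5.2%). The direction can reverse when larger sites do better, and the switch also fires when sites do not differ at all.

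It can also be said that keeping the pooled exact test leaves some inflation in place, since it ran at 4.1-5.2% when site effects were drawn at random. That is fair. It ran at or below 2.5% when each trial's subject proportion was held at the PG, so the answer depends on whether sites are treated as fixed or sampled. A clustered sensitivity analysis would show how much this matters.

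The missing-detail reply does not dispose of the point. Section 19.6 says that the model is to assess the primary objective, and the ordinary output of such a model answers a different question from the hypotheses.

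**Conclusion.** The concern holds in a limited form. Section 19.6 conflicts with Sections 19.10 and 19.11 on the role of the random-centre model. If its intercept is compared with the PG, the target moves from the proportion of subjects to a median-site rate: up by 0.9 to 3.0 points at 89% and by 1.1 to 3.7 points at 73%, for assumed site SDs of 0.5 to 1.0. For efficacy, the plan provides no route for the disease weights behind the PG into the model.

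The effect on pass or fail is not of fixed size or sign. For safety at SD 1.0, false success is about 6-10% with a likelihood-ratio test, about 1-4% with a Wald test, and about 1-5% for the pooled exact test, depending on how the null is simulated. These figures rest on assumed site SDs, site sizes and normally distributed site effects. The efficacy simulations are simplified and show smaller, less certain inflation when site size is unrelated to outcome. The firm conclusion is that a success decision could depend on a parameter and a test that the plan does not name.

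**What to change.** Amend Section 19.6, with matching text in Sections 19.10 and 19.11, to state that:

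- the exact test (safety) and the disease-weighted Z-test (efficacy) remain the primary analyses whatever the pooling result;
- if a pooling test gives p<0.15, a marginal estimate with site-clustered variance (cluster-robust or beta-binomial) is reported as a sensitivity analysis, disease-weighted for efficacy;
- any random-centre logistic model is averaged over sites to the subject-level proportion, with the disease weights for efficacy, before comparison with the PG, and its test is named in advance;
- a trigger in one disease state has a stated consequence for the efficacy sensitivity analysis.

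The cost is SAP wording, slightly more programming, and a somewhat wider sensitivity interval when sites differ. No additional subjects or data are needed.

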19.7. Handling of Missing Data

A sensitivity analysis to the missing data in the ITT sample will be conducted for both the primary safety and efficacy endpoints in the SARS-CoV-2 negative subset and all subjects. The sensitivity analysis will include a best case, worst case and tipping point analysis. The best-case analysis will impute successes for the missing data. The worst-case analysis will impute failures for missing data. The tipping point analysis starts with the best-case analysis and continues until the worst-case analysis is completed, by increasing the number of missing cases imputed as failures by one in each analysis. The goal of the tipping point analysis is to determine at what point the imputation of

failures causes the statistical evaluation of the endpoint to lose statistical significance. If the worst-case analysis maintains statistical significance, the tipping point analysis is not necessary.

19.8. **Summary of Baseline Demographics, Index Procedure Measurements, and Subject Compliance**

Baseline demographics including at a minimum gender, age, and selected medical history will be summarized for ITT subjects overall and in the SARS-CoV-2 – negative subset for primary safety and for primary efficacy. In addition, angiographic characteristics and measurements, as well as procedure characteristics will be summarized.

Subject follow-up and compliance with the protocol will be reported. The number and percent of subjects enrolled, completing study-required follow-ups, and completing the study will be summarized. The subjects who exit the study early will be summarized along with the reason for early study termination.

19.9. **COVID-19 Statistical Considerations**

Given that COVID-19 has been associated with a hypercoagulable state which has the potential to increase MAE occurrence and decrease patency, the study has been modified to test the primary safety and effectiveness hypotheses in both the SARS-CoV-2 negative subset and all subjects (regardless of SARS-CoV-2 status).

The performance goals for both primary safety and primary effectiveness were established based on research in a pre-COVID-19 era and therefore do not account for potential increases in MAEs or decreases in patency associated with SARS-CoV-2 or COVID-19. For each of the hypothesis tests, the current plan is to use the same performance goal in all subjects and in the SARS-CoV-2 negative subgroup given that the potential effects due to SARS-CoV-2 are not well understood. This decision will be revisited prior to analysis of the study data. In the event that additional information becomes publicly available regarding SARS-CoV-2, as related to the VIVID study primary endpoints, we may summarize the major event rate and primary patency in the subject population without and with SARS-CoV-2, and if possible, further based on the extent of COVID-19 illness. Should this information suggest that it may be reasonable to lower the performance goal for the all subject cohort, negotiation with FDA will be pursued given the FDA guidance document, “Statistical Considerations for Clinical Trials During the COVID-19 Public Health Emergency” dated June 2020.

19.10. **Primary Safety Objective**

Subjects Included the Analysis: Subjects who meet the ITT definition.

Endpoint: The primary safety endpoint is freedom from major adverse events (MAEs) at 30 days post index procedure evaluated per subject. MAEs are defined in **Section 6.1** Primary Endpoints.

Performance Goal: Disease state specific PGs were calculated from the point estimates for major bleeding, pulmonary embolism and peri-procedural mortality from Razavi et al¹ converted to freedom from estimates and application of a 10% non-inferiority margin. For example, the expected freedom from the combined primary safety event for nonthrombotic subjects is $100 - (0.3 + 0.2 + 0.1) = 99.4\%$. Therefore, the PG for the nonthrombotic group is $99 - 10 = 89\%$. The same calculation for the acute-thrombotic group results in an 87% PG, $87\% = 100 - (1.1 + 0.9 + 0.7) - 10$. Lastly, the PG for chronic postthrombotic is $88\% = 100 - (0.9 + 0.6 + 0.3) - 10$. Given the similarity of the disease-state specific PGs, it was determined that a disease state specific goal was not necessary. A PG of 89% was adopted for the study in both the SARS-CoV-2 negative subset and overall.

Hypothesis and Performance Goal:

H₀: Proportion of subjects with freedom from MAE (p_{MAE}) is less than or equal to the (PG) at 30 days, $p_{MAE} \leq 89\%$

H₁: Proportion of subjects with freedom from MAE is greater than the (PG) at 30 days, $p_{MAE} > 89\%$

The freedom from MAE proportion will be calculated such that the numerator is the number of subjects in whom a MAE did not occur within 30 days of the index procedure. The denominator is the number of subjects with 30 days of follow-up plus the number of subjects with a MAE prior to 30 days who exited the study prior to 30 days, if any.

Sample Size Rationale: Using PASS 19, a one-sample Exact Test (binomial enumeration), power = 90%, one-sided Type I error controlled at 2.5%, and assumed freedom from MAE of 96.1% with a PG goal of 89%, the required evaluable sample size is 140 subjects.

Primary Statistical Analysis: The primary statistical analysis will be conducted in the FAS subset for the primary safety endpoint overall and in the SARS-CoV-2 negative subset. The primary statistical method is a one-sample exact test comparing the proportion of subjects free from a MAE to the PG using a two-sided $\alpha = 0.05$. The exact two-sided 95% confidence interval for the proportion of subjects free from MAE will be calculated.

The two-sided p-value in the SARS-CoV-2 negative subgroup and all subjects will be calculated and ordered from largest to smallest. If the largest p-value, is statistically significant at $p < 0.05$ then the hypothesis test is statistically significant in both the SARS-CoV-2 negative subset and all subjects. If not, testing continues to the smallest p-value. If the smallest p-value < 0.025 then the hypothesis test is statistically significant in the group for which the smallest p-value is associated with. If the

¹ Razavi MK, Jaff MR, Miller LE. Safety and Effectiveness of Stent Placement for Iliofemoral Venous Outflow Obstruction Systematic Review and Meta-Analysis. Circ Cardiovasc Interv. 2015;8:e002772. DOI: 10.1161/CIRCINTERVENTIONS.115.002772.)

smallest p-value ≥ 0.025 , then the hypothesis test is not statistically significant in either the SARS-CoV-2 negative subset nor all subjects.

Additional Analysis: The evaluation for pooling analyses specified in **Section 19.6** will be completed. If there is missing data for the ITT subjects, the sensitivity to missing data analysis outlined in **Section 19.7** will be completed. Additionally, the primary statistical analysis will be conducted in the per protocol sample overall and in the SARS-CoV-2 negative subset.

